Remote Baseline (Visit 2): Upon completion of the screening process, subjects will be scheduled for the baseline visit which will require approximately two hours. Medication will be mailed directly to the patient's home through appropriate and approved direct-to-patient services. Subjects will be prescribed study drug for the entirety of Trial A (either placebo or LDX) and instructed to begin taking the medication as directed by the study provider. If the participant needs additional study drug in order to complete the trial an additional script will be submitted to IDS for dispensation. The subject will be sent a scale (if needed) and blood pressure cuff for future remote vital sign collections. On the day of the remote baseline visit, subjects will meet remotely with a member of the study team to complete behavioral assessments regarding their mood and emotions and complete cognitive testing.

Week 2 Phone Check-In: At the end of week 2 of medication use, the CRC will check in with the participant by phone to assess for side effects. Subjects who are having more than mild side effects will be instructed to reduce their dose back to one pill per day.

Week 3 Mid-Trial Check-In: Halfway through Trial A, during their third week, subjects will be scheduled for a remote follow-up visit where they will be monitored by the CRC for potential side effects of the medication and medication compliance. If no or mild side effects are reported, subjects will be instructed to increase the study drug to three pills per day. Subjects who are having more than mild side effects will be instructed to reduce their dose back to one pill per day. The study CRC can exercise her discretion regarding medical personnel involvement at this check-in. Subjects will be instructed to complete various mood and symptoms ratings during the visit. In total, the visit will require approximately 60 minutes and will include measures of blood pressure, pulse, and weight.

Week 4 Phone Check-In: During week 4, the CRC will check in with the participant by phone to assess for side effects. Subjects who are having more than mild side effects will be instructed to reduce their dose back to 2 pills per day for the remainder of the trial.

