2.3 Medical Administration

Subjects will be prescribed lisdexamfetamine (LDX) 20mg capsules or a look-alike placebo (microcellulose) by the study PI ([name], M.D.) or her designee. Subjects will be instructed to take one pill (LDX = 20 mg) each morning for 7 days and then will be asked to increase to two pills (LDX = 40 mg) each morning for 14 days. If the study drug is well tolerated by the end of week 3 (as per medication monitoring by the CRC), participants will be asked to increase to three pills (LDX = 60 mg) each morning until the completion of the trial. Participants will be instructed to contact the study team if they experience any side effects and may decrease their medication as instructed. At the end of week 6, which is the end of the trial, participants will be evaluated and instructed to stop their study drug. After an approximate 2-week washout, participants will be crossed over to the other condition and the procedure will repeat. See table below for dosing instructions when the substance is well tolerated.

Week	1	2	3	4	5	6
Dosage	20mg	40mg	40mg	60mg	60mg	60mg

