10.2 Prior Clinical Research Experience

Shire's IND, #67,482, provides important information about LDX, including clinical research experience with human subjects. In addition, the FDA approved prescribing information includes a brief summary of clinical trials of LDX in both children and adults. Pertinent to the present project, the information regarding adults from IND#67,482 is presented here.

A double blind, randomized, placebo-controlled, parallel-group, study was conducted in adults (N=420) who met DSM-IV criteria for ADHD. In this four-week study, patients were randomized to fixed dose treatment groups receiving final doses of 30, 50, or 70 mg of Vyvanse® or placebo. All subjects receiving Vyvanse® were initiated on 30mg for the first week of treatment. Subjects assigned to the 50 and 70 mg dose groups were titrated by 20 mg per week until they achieved their assigned dose. Significant improvements in ADHD symptoms, based upon investigator rating on the ADHD Rating Scale (ADHD-RS), were observed at endpoint for all Vyvanse® doses compared to placebo.

A second study was a multi-center randomized double-blind, placebo-controlled, cross-over design, modified analog classroom study of Vyvanse® to simulate a workplace environment in 142 adults who met DSM-IV TR criteria for ADHD. There was a 4-week open-label, dose optimization phase with Vyvanse (30, 50, or 70 mg/d in the morning). Subjects were then randomized to one of two treatment sequences: 1) Vyvanse® (optimized dose) followed by placebo, each for one week or 2) placebo followed by Vyvanse®, each for one week. Efficacy assessments occurred at the end of each week, using the Permanent Product Measure of Performance (PERMP). The PERMP is a skill-adjusted math test that measures attention in improvement in attention across all post-dose time points, as measured by average PERMP total scores over the course of one assessment day, as well as at each time point measured. The PERMP assessments were administered at pre-dose (-0.5 hours) and at 2,4,8,10,12, and 14 hours post-dose.

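### The week 3 and week 4 dose rules ignore the current dose: a woman cut to 20 mg at week 2 can be told to take 60 mg, and a woman on one pill has no usable week 4 instruction

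*Combined protocol and SAP*

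**What the plan says.** Section 2.3 sets the planned titration. The first step is "Subjects will be instructed to take one pill (LDX = 20 mg) each morning for 7 days", followed by an "increase to two pills (LDX = 40 mg) each morning for 14 days". The move to three pills (60 mg) is conditional: "If the study drug is well tolerated by the end of week 3 (as per medication monitoring by the CRC"). The dose table there (20, 40, 40, 60, 60, 60 mg for weeks 1 to 6) is stated to apply to the well-tolerated course only.

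Section 2.1 gives the check-in rules:

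- **Week 2 call:** "Subjects who are having more than mild side effects will be instructed to reduce their dose back to one pill per day".
- **Week 3 visit:** "If no or mild side effects are reported, subjects will be instructed to increase the study drug to three pills per day". For more than mild effects, the week 2 sentence is repeated. Also: "The study CRC can exercise her discretion regarding medical personnel involvement at this check-in".
- **Week 4 call:** women with more than mild effects are told to "reduce their dose back to 2 pills per day for the remainder of the trial".

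None of these rules mentions the dose being taken when the question is asked. The same procedures apply in Trial B.

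**The concern.** The rules work for a woman who follows the planned course: two pills at week 3, three at week 4. They do not work for a woman who has already been cut back.

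First, feeling better on a reduced dose is what the week 2 cut is meant to achieve. Under the week 3 rule, that improvement triggers an increase to a dose above the one that caused the cut.

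Second, the week 4 rule has a single target, two pills. For a woman on one pill, that is not a reduction.

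What is at stake is the safety of women who have already shown poor tolerance. Section 5.1 notes that lisdexamfetamine can raise blood pressure and heart rate, and that serotonin syndrome risk increases with serotonergic drugs. Section 3.4 allows SSRIs and SNRIs. Section 5.1 also relies on careful monitoring to limit serious side effects, so the dose rules should be safe when followed to the letter.

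**Working it through.** The plan gives no figure to reproduce on this point. The check applies the written rules to every possible course.

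**Inputs.** One pill is 20 mg; one pill on days 1–7, then two pills (section 2.3). Check-in rules for weeks 2, 3 and 4 (section 2.1). Treatment ends at day 42 (six weeks).

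**All eight courses.** N = no or mild side effects; M = more than mild. Each woman reaches the week 2 call on two pills.

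| Wk 2 | Wk 3 | Wk 4 | Pills after wk 2 | after wk 3 | after wk 4 |
|---|---|---|---|---|---|
| N | N | N | 2 | 3 | 3 |
| N | N | M | 2 | 3 | 2 |
| N | M | N | 2 | 1 | 1 |
| N | M | M | 2 | 1 | undefined |
| M | N | N | 1 | **3** | 3 |
| M | N | M | 1 | **3** | 2 |
| M | M | N | 1 | 1 | 1 |
| M | M | M | 1 | 1 | undefined |

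**Path (a): M at week 2, N at week 3 (two of the eight courses).**

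- Days 8–14 at 40 mg (about 7 days), then at most about 7 days at 20 mg (days 15–21), then 60 mg.
- Step: 60 − 20 = 40 mg.
- Relative to the planned step: 40 / 20 = 2 times.
- Relative to the current dose: 60 / 20 = 3 times.
- Relative to the dose that led to the cut: 60 / 40 = 1.5 times.
- Comparison within the protocol: in the adult fixed-dose trial in section 10.2, the higher-dose groups were "titrated by 20 mg per week until they achieved their assigned dose". The 40 mg step is twice that.
- If she has more than mild effects at week 4 (days 22–28), she is put on 40 mg to day 42: from 42 − 28 = 14 days to 42 − 22 = 20 days.

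**Path (b): on one pill at week 4 with M (two of the eight courses).** The stated target, two pills (40 mg), is above her 20 mg. The wording about reducing back shows the rule was written for women on three pills, so the sensible reading is that her case is undefined, not that she should be raised. For a woman already on one pill at week 3 and still unwell, the week 3 instruction to go to one pill also changes nothing.

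**Would supply stop the jump?** No. Section 2.4 provides one bottle meant to last the six weeks. The planned course uses 7 × 1 + 14 × 2 + 21 × 3 = 98 capsules. Path (a) without a week 4 cut uses 7 × 1 + 7 × 2 + 7 × 1 + 21 × 3 = 91. If the bottle is filled for the planned course, she already has the capsules and no dispensing step intervenes.

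**The case against.** The strongest reply is that section 2.3 is the dosing section and makes three pills conditional on good tolerance through week 3, after 14 days at two pills. A woman cut at week 2 did not have that course, so she could be read as excluded. That reading is possible. But the sentence names no dose, and section 2.3 gives no alternative schedule for her. The rule the coordinator would apply at the visit looks only at side effects reported then.

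Clinical direction also exists. The drug is taken as the study provider directs, participants are told to report side effects and may decrease when instructed, the principal investigator monitors safety, and staff meet weekly on adverse events (sections 2.1, 2.3, 5.4). This makes mechanical use of the rule less likely. It does not supply the missing rule. The week 3 vital signs are taken on the reduced dose, clinician involvement at that visit is optional, and the week 4 call comes after the increase. No further check-in is described before the end-of-trial visit.

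Several points on weight stand. 60 mg is within this trial's range and below the 70 mg arm in section 10.2. The woman has already had about a week at 40 mg. More than mild effects may be transient. Nothing in the documents shows harm from a 40 mg step. Each woman is exposed to active drug in only one of her two periods. Path (b) is a minor omission.

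**Conclusion.** The concern holds. Followed literally, the week 3 rule takes a woman from 20 mg to 60 mg in one step after more than mild side effects on 40 mg, and section 2.3 does not clearly prevent it. The week 4 rule leaves a woman on one pill without an instruction.

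The conclusion rests on the check-in rules being applied as written and on the planned schedule up to the week 2 call. The documents do not say how often women will be cut at week 2. Each 1% of the 100 women who follow path (a) while on lisdexamfetamine is one woman. The gap is confined to women with early poor tolerance and does not enter the sample size or the analysis. It should be corrected because the rule itself, not only its coverage, gives the less safe result.

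**What to change.** State each instruction by current pill count in section 2.1, and use the same wording for the week 3 step in section 2.3. A workable version, with exact steps for the investigators to confirm:

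| Check-in | Pills now | No or mild effects | More than mild effects |
|---|---|---|---|
| Week 2 | 2 | stay at 2 | reduce to 1 |
| Week 3 | 2 | increase to 3 | reduce to 1 |
| Week 3 | 1 (cut at week 2) | stay at 1, or rise to 2 at most, with study clinician input | stay at 1 or stop, after clinician review |
| Week 4 | 3 | stay at 3 | reduce to 2 |
| Week 4 | 2 (raised again after a cut) | stay at 2 | reduce to 1 |
| Week 4 | 1 | stay at 1 | stay at 1 or stop, after clinician review |

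If a shorter change is preferred, two clauses remove the main fault: limit the week 3 increase to women currently taking and tolerating two pills, and limit the week 4 reduction to women on three. The one-pill case would then still need a line of its own.

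The cost is a few sentences and an update to any working instructions the coordinators use, with no added visits or patients. Some women would finish at 20 or 40 mg instead of 60 mg; both lie within the 20 to 60 mg range already given in section 2.1.

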2.1 General Design

To further our understanding of the mechanism of LDX treatment in women with executive function complaints after risk-reducing bilateral salpingo-oophorectomy (RRSO), participants will undergo multi-modal imaging (fMRI and 1H-MTS at 7 Tesla) pre- and post- a 6-week course of LDX (20-60mg/d) or placebo followed by an approximate 2-week washout before crossing over to the other condition. This study utilizes a double-blind, placebo-controlled, cross-over design. We will recruit 100 women who are between the ages of 35 and 58 years old. Subjects will be recruited from flyers posted around campus, paid advertisements, referrals from collaborators at FORCE (Facing Our Risk of Cancer Empowered), the Basser Center, and other medical settings where women who have undergone RRSO may seek treatment. Study subjects will be screened by a member of the research staff who can gauge whether the individuals are likely to meet study criteria. Potential participants who appear to meet criteria and express an interest in the study will have the option of completing the screening visit remotely or completing the visit in-office. Participants will also have the option to complete a remote version of the study.

In-Office Screening: Participants who report for an in-office screening will be presented with the full, written ICF where they will have the chance to review and sign it with the study CRC. After giving full, written informed consent, subjects will undergo screening for past and current psychiatric disorders with the Mini International Neuropsychiatric Interview (M.I.N.I) and complete several behavioral ratings and questionnaires concerning personal history. A urine sample will be collected from participants to do a urine drug screen. Subjects will then undergo a brief medical evaluation and electrocardiogram (EKG) conducted by the study PI ([name], M.D.) or key study personnel. Vital signs including blood pressure and pulse will be recorded. Women with a consistent systolic blood pressure of >145mm Hg or diastolic blood pressure >90 mm Hg after three readings at screening will not be enrolled and referred to their primary care doctors for further evaluation. Routine laboratory studies will include TSH, FSH and estrogen assays. If potential subjects have had these tests performed within the previous 6 months and can present their results, they will forgo additional blood work except that for genetics studies (4 mL)

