Participants either unable to travel or unable to complete an MRI will be offered a remote non-imaging alternative which removes the MRI and blood draws from the required study procedures.

Baseline MRI Scan (Visit 2): Upon completion of the screening visit, subjects will be scheduled to undergo their baseline ¹H-MRS and fMRI scan session, which will take approximately 75 minutes. Subjects will be instructed to present to the Penn Center for Women's Behavioral Wellness approximately 2.5 hours before their scheduled scan to complete behavioral assessments regarding their mood and emotions and to complete out-of-scanner cognitive testing. Subjects will then be escorted to the Center for Magnetic Resonance and Optical Imaging (CMROI) by the study CRC where they will be scanned and asked to perform a series of tasks assessing their memory and attention. Subjects will then be given the study drug for the entirety of Trial A (either placebo or LDX) and instructed to begin taking the medication as directed by the study provider. If the participant needs additional study drug in order to complete the trial an additional script will be submitted to IDS for dispensation. Upon completion of the visit, the subject will be given a scale and blood pressure cuff for future remote vital sign collections. In total, the baseline scan visit will require approximately 4 hours to complete.

Additional Study Procedures for MRI eligible Subjects who Completed Screening Remotely: All subjects who completed the screening visit remotely will be reminded to bring the original version of the ICF to their Baseline MRI Scan (Visit 2) so that the original copy can be stored at PCWBW. A urine sample will be collected from all subjects to do a urine drug screen and an additional tube of blood will be collected for those who consented to genetics studies (4 mL) on the ICF before they start their scan. Subjects who indicated that they prefer research personnel to complete their required EKG and medical evaluation will be instructed to present to the Penn Center for Women's Behavioral Wellness approximately 3.5 hours before their scheduled scan to complete said procedures in addition to the assessments stipulated by Visit 2. In total, the baseline scan visit will require approximately 5 hours to complete for those that still need medical clearance.

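### Blood pressure and pulse are measured at the week 3 visit but do not govern the dose increase made there, and the rule allows a jump from 20 to 60 mg

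*Combined protocol and SAP*

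**What the plan says.** The week 3 visit is remote and run by the CRC. Section 2.1 gives it two dose outcomes. One is an increase: "If no or mild side effects are reported, subjects will be instructed to increase the study drug to three pills per day". The other is a reduction: "Subjects who are having more than mild side effects will be instructed to reduce their dose back to one pill per day". The reduction instruction also appears for the week 2 call.

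Section 2.3 describes the increase to three pills with a different condition: "If the study drug is well tolerated by the end of week 3 (as per medication monitoring by the CRC").

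The Section 2.1 paragraph says the visit "will include measures of blood pressure, pulse, and weight". On medical input it says: "The study CRC can exercise her discretion regarding medical personnel involvement at this check-in".

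Section 5.1 names a rise in blood pressure and heart rate as an effect of LDX, and lists careful monitoring among the means of keeping serious side effects down. The only numeric blood pressure limit is systolic above 145 or diastolic above 90 mm Hg, persisting over three readings. It is written for screening (Sections 2.1 and 3.4). No pulse limit appears anywhere. Trial B repeats the Trial A medication procedures.

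**The concern.** Raised blood pressure often has no symptoms. A step-up rule keyed to what the participant reports can miss a drug effect that the protocol itself names, at the visit where the dose rises and with the reading already in hand. Screening cannot fill this gap, because screening readings come before any exposure to the drug.

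The rule also names a destination (three pills) and not an increment. It does not take account of the dose a woman is on when she reaches week 3.

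What is at stake is participant safety during the last three weeks of each LDX period. The estimate of treatment effect is not in question.

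**Working it through.** The plan states no figure to reproduce. The check sets the relevant sections side by side and follows two participants through the rule.

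**What is attached to the week 3 readings**

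| Element | Where it could appear | What is there |
|---|---|---|
| Numeric limit | 2.1, 2.3, 3.4, 5.1, 5.4 | Screening only (145/90); none on treatment; none for pulse |
| Repeat reading | 2.1, 3.4 | Three readings, screening only |
| Dose hold tied to vital signs | 2.1, 2.3 | None |
| Physician review before the step | 2.1, 5.4 | CRC discretion; weekly staff meeting not linked to the step |

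**Participant A: no symptoms, high reading.** She takes two pills (40 mg) and at week 3 reports no side effects, but her reading is above 145/90. Under Section 2.1 the condition for an increase is met, so she goes to three pills: 60 − 40 = 20 mg more. Under Section 2.3 the answer turns on whether the CRC counts the reading against tolerability, and the text does not say. Nothing requires a second reading or a call to a physician.

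**Participant B: cut at week 2.** She has more than mild side effects at the week 2 call and is reduced to one pill (20 mg). By week 3 they are mild or gone. Section 2.1 then sends her to three pills: 60 − 20 = 40 mg, or two capsules at once. The schedule table in Section 2.3 (20, 40, 40, 60, 60, 60 mg) never moves by more than 20 mg, so this jump looks unintended.

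**Other on-drug contacts.** Each trial has four: the week 2 call, the week 3 visit, the week 4 call and the end-of-trial visit. Blood pressure is explicitly listed at one of the four, week 3. More readings may be taken: at Visit 2 "the subject will be given a scale and blood pressure cuff for future remote vital sign collections", and Section 2.3 adds "At the end of week 6, which is the end of the trial, participants will be evaluated and instructed to stop their study drug". None of these is specified, and none comes with an action.

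**How often the rule is applied.** 100 women × 2 trials = 200 week 3 decisions, 100 on LDX and 100 on placebo. If the 10% drop-out in Section 3.1 all falls before the first decision, 90 × 2 = 180. These are counts of decisions, not of high readings; the documents give no blood pressure distribution from which to derive the latter.

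**The case against.** The strongest reply is that the rule already takes in vital signs. Section 5.1 discusses blood pressure and heart rate in its side-effect text. Section 2.1 has the CRC monitoring for side effects at the same visit as the readings. Section 2.3 asks for tolerability, not merely absence of complaints. On that reading a sensible CRC would weigh a high value and call a physician. This stands in part: the protocol permits that conduct, and a reader who inferred that readings are ignored, or that a woman with a high one must be stepped up, would go too far.

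A reader might also infer from Section 2.1 alone that the same reading leads to either 60 or 20 mg, a three-fold difference, with no way to stay at 40 mg. Section 2.3 does not support that: if the drug is not well tolerated, the increase simply does not apply. Nor does the amount of drug taken after week 3 measure risk; it is schedule arithmetic.

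The surrounding safeguards are real:

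- Section 3.4 excludes known heart disease, a clinically significant abnormal EKG, uncontrolled hypertension and persistently high screening readings.
- Section 5.1 says LDX is not contraindicated in stable hypertension.
- The 60 mg ceiling is below the 70 mg arm of the adult trial in Section 10.2, which also moved in 20 mg steps, and did so weekly.
- The investigator is the primary safety monitor, and staff discuss adverse events and data weekly (Section 5.4).
- Participants are told to call about side effects, and the week 4 call can return a woman to two pills.

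These lower the risk. None requires anyone to act on a high reading before the dose instruction is given, and the last two depend on side effects being noticed and reported.

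**Conclusion.** The gap is real and narrow. As written, the week 3 increase can be given to a symptom-free woman with high blood pressure or pulse, and to a woman on 20 mg in a single 40 mg jump. Action on the reading is allowed but not required.

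The size is bounded on one side only. The step is 20 mg on the standard schedule and 40 mg after a week 2 reduction, within the planned maximum of 60 mg and in a population screened for cardiovascular risk. How often a high reading would occur, and with what harm, cannot be estimated from the documents, and no rate is claimed.

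The conclusion rests on the protocol text alone; consent forms were not available. It assumes only that a high reading can occur without reported symptoms. It is a cheap improvement for participant safety. A reader might extend it to a threat to validity or power, but nothing in the documents supports that.

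**What to change.** In Sections 2.1 and 2.3, for both trials:

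1. Take blood pressure and pulse before giving the week 3 dose instruction.
2. If either exceeds an investigator-set limit (for example the protocol's own 145 systolic or 90 diastolic, plus a pulse limit), repeat to three readings.
3. If still high, keep the current dose until a blinded study physician has reviewed it. This referral is not left to CRC discretion.
4. State that good tolerability includes these readings.
5. Limit any week 3 increase to one capsule above the current dose.

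The rule for more than mild side effects stays as it is.

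The cost is a few sentences and a line on the week 3 form. The readings, home cuffs and a study physician are already in the plan, and a hold at 40 mg lies inside the range in Section 2.1: "a 6-week course of LDX (20-60mg/d) or placebo followed by an approximate 2-week washout". The downside is occasional physician calls and some delayed or omitted steps to 60 mg. Because LDX can raise blood pressure, holds would probably fall more often in LDX than in placebo periods and slightly lower active exposure overall. For one woman held at 40 mg throughout weeks 4 to 6 on LDX, the reduction is 21 days × 20 mg = 420 mg out of 7 × 20 + 14 × 40 + 21 × 60 = 1,960 mg, or 21% of that trial's total. The investigator may prefer an on-treatment limit different from the enrolment one; what matters is that a limit is written.
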